### **Setting.**

The N-CTRC, located at Western Psychiatric Institute and Clinic (WPIC), will be the site for all sleep studies (see letter of support [name]) for University of Pittsburgh recruited. The setting for all assessments will be the VAPHS for subjects recruited there. . Montefiore Hospital CTRC (MUH-CTRC) will be the site for all University of Pittsburgh recruited participants.

West Virginia University: Subjects will be consented and undergo study procedures at the WVU Medicine outpatient clinics (Sleep Evaluation Center, Medical Group Practice, Family Medicine, and Medical Specialties clinics), and the Clinical Trials Research Unit.

**Study Measures.** (See Appendix for copies of instruments). We selected the self-report and physiological measures to reflect the key behavioral domains that are adversely affected by OSA and EDS as documented by numerous published studies. They provide a comprehensive assessment of treatment response and the basis for secondary analyses and hypothesis generation. The tests are organized to reduce subject burden. Data from the pilot study indicate that the clinical assessments can be completed in < 1 hour, and questionnaires can be completed in the subject's home at their leisure. We recognize the need to decrease subject burden and have reduced the number of visits by having the subjects' return their devices (ApneaLinkPlus®, Body Media SenseWear Pro Armband®) by mail, a strategy that was successful in the pilot/feasibility study.

### **Screening Measures:**

**Screening interview.** Respondents to recruitment solicitations will undergo a brief interview (in-person or telephone) to determine if they meet initial eligibility criteria. The interview includes the MAP Index.

Multivariable Apnea Prediction (MAP) Index will be used to identify persons at moderate-to-high risk for OSA. The MAP uses the frequency of snoring, breath holding, and snorting, age, sex, and self- reported height and weight to determine the likelihood of OSA. The MAP estimates using multiple logistic regression; its positive predictive ability of AHI $\geq 10$  in patients presenting at sleep disorders centers was 0.79 (p<0.0001).

ApneaLinkPlus® is an FDA approved level III device for in-home unattended sleep studies (see Figure 3). Previous studies found the device to be highly sensitive and specific to diagnose moderate-to-severe OSA. The clinical guideline by the Portable Monitoring Task Force of the American Academy of Sleep Medicine concluded that level III portable devices were appropriate for the diagnosis of OSA in patients with a high pretest probability of moderate-to-severe sleep apnea. The older single channel ApneaLink was evaluated in determining the presence and severity of OSA in a recent study by Drs. [name] and [name]. In a sample (mean age  $45.1 \pm 11.3$ , 55% female, BMI  $35.9 \pm 9.1$ ) that will be similar to ours, the ApneaLink had a sensitivity of 79.0% and specificity of 88.2% for detecting an AHI  $\geq 15$ ; for an AHI $\geq 20$  the sensitivity was 100.0% and specificity 92.5% compared to a simultaneous in-laboratory polysomnography. The ApneaLinkPlus® that we will use is a 4-channel device that records breaths, respiratory flow, oxygen saturation and pulse rate. We will ask enrolled participants to wear the ApneaLinkPlus® for a single night to identify those persons with  $\geq 10$  apneas/hour. The ApneaLinkPlus® has scoring software version v9.2 that analyzes data. Drs. [name], [name] (University of Pittsburgh/VAPHS), or [name] (West Virginia University) will review all ApneaLinkPlus® studies. At the John Dingel VAHS, a similar FDA approved level III device, the NOX-T3, will be used. This device provides the same metrics as the ApneaLink Plus®.

## Primary Dependent Measures

**Aim 1: Glycemic control.** Objective measures of glycemic control are 1) A1C and 2) serum fructosamine  
a. The A1C (5 cc serum sample) offers a stable indication of glycemic control over the past 2 to 3 months. The American College of Endocrinology suggests a goal of an A1C of 6.5% or less. We will utilize the use of only standardized, in-laboratory validated assays for A1C testing.

b. The fructosamine level (5cc serum sample) measures glycation of serum proteins, it is responsive to changes in the patient's average glucose because the half-life of albumin (about 20 days) is of shorter duration than the A1C. This test will show any change in glycemic control over the last 2 to 3 wks. (*Optional measure, not done at WVU*)

**Aim 2: Diabetes self-management behavior**

a. The Diabetes Knowledge Test (DKT) We will use the first 15 items for subjects who do not use insulin and the additional 3 on insulin usage for subjects who are prescribed insulin. The psychometric properties of the items yield an alpha  $\geq 0.70$  for the general test and the insulin-use subscale, which indicates that both are reliable. The DKT takes approximately 5-10 minutes to complete.

b. The Summary of Diabetes Self-Care Activities (SDSCA) is a brief questionnaire about diabetes self-management that includes items assessing the following aspects of the diabetes regimen: general diet, specific diet, exercise, blood-glucose testing, foot care, and smoking. This validated instrument has high inter-item correlations within scales (mean  $r = 0.47$ ), with the exception of specific diet; test-retest correlations were moderate (mean = 0.40). It takes 5-10 minutes to complete.

c. Removed the Diabetes Care Profile (DCP) from protocol.

d. The Body Media SenseWear Pro Armband® provides an objective measurement of physical activity. It was used successfully in the pilot/feasibility study and will be used to obtain 7-day 24-hour activity counts. The Body Media SenseWear Pro Armband® measures the duration and intensity of activity (daily total energy expenditure, number of steps walked, average metabolic equivalent, active energy expenditure) individuals. It was found accurate in measuring sedentary to high-impact activity; it collects data on sleep duration which can be evaluated along with the sleep diary. The armband allows activity not captured directly, such as water aerobics, to be manually entered; the software then utilizes an algorithm to determine the energy expenditure. The data will be uploaded to a computer, minimizing the potential for recording errors. The activity endpoint will be summarized as the subject's mean daily activity count on days when the monitor is worn  $\geq 20$  hours. (At site WVU, the BodyMedia SenseWear Pro Armband® is not used. A pedometer will be used to obtain the steps walked).

e. The Problem Areas in Diabetes (PAID) will be used to assess emotional distress related to diabetes management and how it is affected by OSA and EDS. The PAID comprises 24 items on a 5-point Likert scale that are summed to provide a total score of emotional distress, with higher scores denoting greater distress. The internal reliability is  $>0.90$ ; it has sound concurrent validity as determined by moderate to strong correlations with a range of theoretically-related measures, and responsiveness to change during brief psychosocial and educational interventions. Welch et al. showed effect sizes between .30 and .65 for the PAID across seven different intensive diabetes psychosocial, educational, and medical interventions, indicating good responsiveness. The PAID has demonstrated validity among minority urban patient populations. It takes 5-10 minutes to complete.

## Secondary Dependent Measures:

a. Sleep Quality. The Pittsburgh Sleep Quality Index (PSQI) is a validated questionnaire that measures the quality, duration, and patterns of sleep in adults. It differentiates "poor" from "good" sleep over the past month. A global sum of 5 or more indicates a poor sleeper. The PSQI has a Cronbach's alpha of .83 and a test-retest correlation coefficient of 0.85. The PSQI takes 5 minutes to complete.

b. Subjective Sleepiness. The Epworth Sleepiness Scale (ESS) is an 8-item scale that measures subjective daytime sleepiness, respondents are asked to rate the likelihood of falling asleep in situations using a 4-point Likert scale ranging from 0 ("never dozing") to 3 ("high chance of dozing"). The ESS has test-retest reliability ( $r=.82$ ) and internal consistency (Cronbach's alpha =.88) . The ESS at  $\geq 10$  has a sensitivity of 93.5% and a specificity of 100% for distinguishing pathological sleepiness. The ESS takes 2-3 minutes to complete.

c. Mood. The Profile of Mood States (POMS) is a reliable and valid measure of mood states that has been shown to be sensitive to sleep deprivation and to CPAP treatment of apnea. It presents 65 adjectives to rate (1 to 5) feelings during the last 7 days. The POMS takes 5 – 10 minutes to complete.

d. Vigilance. The Brief Psychomotor Vigilance Test (PVT-B). will assess vigilance before and after each DEC session. The PVT-B is a computer-based reaction time test that was recently developed to evaluate the ability to sustain attention and respond in a timely manner to a signal during a 3-minute testing session. There is no difference in sensitivity to sleep loss between the PVT and the PVT-B with the lapse threshold reduced from 500 to 355ms. Total lapses, false starts, and reaction time will be the outcome measures of the PVT-B.

e. Diabetes Empowerment Scale-Short Form measures the psychosocial self-efficacy of people with diabetes. In order to allow for a brief overall assessment of diabetes related psychosocial self-efficacy, an eight-item short form of the DES (the DES-SF) was developed. The DES-SF was created by choosing items from the original 37 items. The reliability of the DES-SF using the original data set was alpha = 0.85.

#### **Additional measures: Demographic, Anthropometric Measures, and Process Measures.**

- a) Sociodemographic and Lifestyle Questionnaire. Sociodemographic information will be obtained by a questionnaire developed for the Center for Research in Chronic Disorders at the University of Pittsburgh.
- b) Health History Questionnaire is a revision of the Charleson Comorbidity Index to capture key information related to comorbid conditions and specific questions of interest such as duration of T2DM and medications
- c) BMI/ Body Composition. Height will be measured at baseline. The Tanita-300GS Scale and Body Fat Analyzer will be used to weigh subjects and determine body composition. (Regular scale used to weight subjects at WVU)
- d) AADE7 Goal Sheet will be used by the CDE to evaluate progress of self-care activity.
- e) Newest Vital Sign (NVS) serves as a screening test for limited health literacy. The NVS is administered using an enlarged, laminated food label that requires interpretation of the information and basic calculations of percent calories and fat (we will offer paper/pencil for calculation); less than 4 correct answers indicate the possibility of limited health literacy.
- f) Adherence. EncoreAnywhere™ will be used in the CPAP machines to measure adherence. EncoreAnywhere will be used to measure adherence. The online adherence data will be at least twice during the first week and then weekly. Because increased doses of CPAP are associated with improved daytime functioning, we plan to encourage subjects to be adherent to CPAP/sham-CPAP all-night, every night. We will objectively measure the pattern of CPAP adherence to determine if the subject is a “good user” or “slowly improves” or has less than optimal use and requires focused CPAP support to assist with improved CPAP usage. If we are unable to use the Encore Anywhere device, we will verbally ask participants how many hours they have used the device and check for adherence with data automatically collected in the devices memory that can be downloaded and read from the SmartCard.
- g) Activity monitoring will be measured with Omron pedometers. Mean steps walked with the pedometers will be compared to individualized goal for steps based on baseline status during the DEC sessions.
- h) Sleep/Activity Diary will be used to record subjective sleep quality and duration, daytime sleepiness, and sleep habits.
- i) Food Diary will be used to record dietary intake for 3 days before the DEC. Diet data will be used by the Diabetes Educator to provide participants feedback and help improve eating behaviors.
- j) Connor Diet Habit Survey (Connor DHS) will assess eating habits and diet composition. The Connor DHS is a 38-item multiple-choice questionnaire comprised of 5 sub-scales: (a) cholesterol-saturated fat, (b) carbohydrate, (c) beverage, (d) salt, and (e) restaurant eating and recipes. Validity of the DHS was established previously with 24-hour dietary recalls ( $r = .33$ ,  $p <.01$ ). The Connor DHS requires about 5-10 minutes to complete. The Connor DHS will be used at baseline and 6 months.
- k) Rapid Eating and Activity Assessment for Patients (REAP). is a dietary assessment tool to briefly assess patient's diet and physical activity. The REAP is a validated instrument with test-retest reliability ( $r=.86$ ,  $p<.001$ ) and convergent reliability with the Healthy Eating Index score ( $r=.49$ ,  $p<.0007$ ). This instrument takes about 10 minutes to complete.
- l) SF-12v2 Health Survey is a short (12 questions) version of the SF-36v2® Health Survey that measures a patient's subjective functional health and well-being. The SF-12v2 is a reliable and valid instrument that contains the same structure as the SF-36v2 with Component Summary Measures (Physical Health and Mental Health) and Scales (Physical Health: Physical Functioning, Role-Physical, Bodily Pain, General Health; Mental Health: Vitality, Social Functioning, Role-Emotional, and Mental Health). The SF-12v2 takes approximately two to three minutes to complete.
- m) Stanford Sleepiness Scale. Sleepiness varies during the day. The Stanford Sleepiness Scales, a single question that queries sleepiness on a 1-10 scale, is a validated measure of sleepiness or alertness at a specific moment in time. It will be asked before and immediately after each diabetes educational/counseling session.

#### **Procedures**

**Assessment 1.** Written and verbal explanation of the purpose, protocol, risks and benefits of the study will be provided and informed written consent will be obtained. The subject's ability to read at the 5th grade reading level and comprehend information will be evaluated with questions that ask “if you feel sleepy, should you drive a car or use dangerous machines?” Health literacy will be evaluated by the Newest Vital Sign. A urine pregnancy test will be done, if appropriate. Study staff will perform anthropometric measurements (height, weight, body composition) and a

venipuncture to obtain no more than 30 cc blood for A1C, fructosamine, and lipid profile. Waist circumference will be measured twice with an inelastic measuring tape. The Project Manager/ Study Coordinator will instruct subjects on how to wear the ApneaLinkPlus® device that night when they go to sleep. Subjects' will be instructed on wearing the SenseWear Armband® and filling out the Sleep/Activity/Diet Diary when they wake up and before bedtime for the next 7 days. Subjects will be instructed how to complete the questionnaires at home during the next week. They will be given two padded pre-paid mail packets: the first for returning the ApneaLinkPlus® the next day and the second to return the SenseWear Armband, questionnaires, and the Sleep/Activity /Diet Diary after using them for 7 days. Data from the ApneaLinkPlus® will be uploaded and data reviewed by either Drs. [name] or [name] (at Pitt/VAPHS) or [name] (at WVU) to determine the AHI. When the ApneaLinkPlus® is uploaded, if there is inadequate data to determine AHI eligibility, we will contact the participant and ask if they would be willing to repeat the ApneaLinkPlus® at home sleep study.

History and Physical. Subjects will have a history & physical by a Nurse Practitioner or Medical Fellow to determine if there is any factor that may exclude them from the study. Drs. [name], [name] or [name] will determine if subjects meet all study criteria for randomization.

Randomization. Subjects who meet all inclusion/exclusion criteria will be randomly assigned by computer program (R-track®) using a minimization algorithm with equal allocation to one of two treatment groups: 1) active CPAP set at a level of pressure that will abolish nocturnal respiratory disturbances, or 2) sham-CPAP (placebo) where the level of pressure will not abolish nocturnal respiratory disturbances. Use of a minimization algorithm will insure treatment balance on three factors: 1) the participant's baseline physical activity levels in terms of mean number of steps per day based on the SenseWear Armband® ( $< 5,000, \geq 5000$ ), 2) whether the subject had previous diabetes education, and 3) whether the subject is prescribed insulin. Minimization is a form of adaptive treatment allocation in which the probability of assignment to the treatment groups does not remain constant, but is determined by the current balance and/or composition of the groups. Treatment group assignment will be generated and stored in a secured database. Subjects and all research team personnel involved in further data collection will be blinded as to which group the subjects are assigned. The University of Pittsburgh site will randomize participants from all the recruitment sites (West Virginia University, VAPSHS, University of Pittsburgh).

CPAP Titration Study/Sham-CPAP Titration. The nighttime CPAP titration PSG will be performed in to determine the optimal level of CPAP needed to eliminate the subject's apnea. The CPAP titration PSG will be performed using standard techniques, with effective CPAP level defined as an AHI  $<5/\text{hr}$  with the minimum effective pressure for each subject. Subjects randomized to the sham-CPAP arm will have titration studies that are performed identically to the CPAP titration except the standard CPAP hose will be replaced with the sham-CPAP hose, the modified expiratory valve will be attached and pressure at the nose mask will be  $\leq 1 \text{ cm H}_2\text{O}$ . The sham CPAP blower will be set at a pre-set level where pressure is not transmitted to the subject but produces the blower sound. Subjects will be loaned, without charge, either the CPAP or the sham-CPAP machines to take home for 12-wks. Subjects and their bed partners' will be instructed by the Sleep Educator on how to improve their sleep hygiene, OSA and CPAP therapy. Subjects will be encouraged to use CPAP/sham-CPAP every night; adherence will be monitored weekly with the EncoreAnywhere™ system.

Diabetes Education/Counseling. The DEC will consist of two (2) one-on-one sessions (a 90 minute session and a 60 minute session), and a minimum of 3 follow-up phone calls of approximately 15-30 minutes with a diabetes educator that will start approximately one week after subjects have started CPAP or sham-CPAP. (see Appendix for Curriculum). Subject education will be provided using published educational materials from the American Diabetes Association and the American Association of Diabetes Educators. Partners will be encouraged to attend the sessions. Data from a RCT suggests that 3 1-hr individual sessions results in significantly (p-values  $<.05$ ) decreased A1C and stress associated with diabetes management compared to 8-hrs of group sessions. Although the content will be interactive and tailored to match each individual's needs and cultural influences, all subjects will receive standardized DEC based on the AADE patient competencies (AADE7). Subjects will be provided a pedometer to wear each day and a daily goal of steps, which will be increased over the 12 weeks to reach at least 7,500 steps per day. They will be given 7-day paper diaries and asked to record their daily food and beverage intake, physical activity and sleep habits. The diabetes educator will review the diaries at each of the two intervention sessions; will provide written and oral feedback on progress made toward improving their eating and physical activity habits. Subjects will be instructed on the value of self-monitoring diet and exercise to monitor progress to their behavior change goals. Subjects will be questioned on sleepiness before and after the session with the Stanford Sleepiness Scale. Vigilance will be tested before and after each DEC session with the

PVT-B. (Clarification in protocol 7.25.2018): The Stanford Sleepiness Scale is a part of the PVT-B Vigilance test. The West Virginia University site does not perform the PVT-B testing.

Promotion and Assessment of CPAP Adherence. Our goal is for subjects to use their CPAP/sham CPAP all night/every night. We will enhance the procedures for the promotion of adherence that we employed successfully during the pilot/feasibility study. The education was refined from the protocol developed by Dr. [name]; she will be assisting this proposal as a Consultant. We will utilize motivational enhancing problem solving and review and reinforce principles of good sleep hygiene. Subjects will receive education prior to starting CPAP therapy, e.g., that comfort is improved with the use of heated humidification on CPAP machines. All subjects will be shown various masks and permitted to select the most comfortable mask interface. Brochures will be developed in simple language describing the study and stressing the importance of using the treatment every night. CPAP adherence will be encouraged with a phone call to the subjects by a Sleep Educator after the first night of home use. A refinement from the previous study will be that a Sleep Educator will evaluate CPAP/sham-CPAP adherence nightly for the first 2 nights then at least twice weekly with the EncoreAnywhere™ web-based patient compliance system. The Sleep Educator will phone the subjects at least weekly, and intervene to increase adherence.

**Assessment 2.** An assessment will be done after 6-wks of CPAP/sham-CPAP use. Subjects will be mailed the questionnaires, SenseWear Armband® and the Sleep/Activity/Diet Diary to use for 7-days. They will return to the study site with these items and their glucose meter and pedometer. The assessment includes anthropometric measurements and a venipuncture to obtain no more than 30 cc blood for A1C, fructosamine and lipid profile.

**Assessment 3 with Unblinding/ Debriefing.** (week 12- of CPAP/sham-CPAP use). Subjects will be sent the questionnaires, the SenseWear Armband® to use for 7-days before returning for Assessment #3. Subjects will return to the study site with those items, their glucose meter and pedometer. In addition, they will bring their CPAP/sham-CPAP machines and masks. Anthropometric measurements and a venipuncture to obtain fructosamine, A1C, and lipid profile will be done. Prior to being informed of his/her treatment condition, the subjects will be asked to which arm of the study they think they were assigned. The Project Manager/ Study Coordinator and/or PI will debrief the subject, answer any questions and provide a copy of their sleep and laboratory data.

Crossover to Active CPAP. The crossover to active CPAP is important because of two reasons: 1) ethical considerations and 2) the pilot/feasibility study subjects identified the possibility of eventually being able to try CPAP treatment was a major reason they considered participating in the study. VAPHS subjects who were in either the active and sham-CPAP group will be directed to the Sleep Center at the VAPHS for follow-up care. Non-VAPHS subjects in the sham-CPAP group will be offered the chance to have an actual CPAP titration study, as described above, receive the CPAP education and monitoring, and start CPAP.

**Assessment 4.** (week 24) All subjects are reassessed as described above; it is the final assessment for those who were initially on active CPAP. We will provide those subjects with a summary of their sleep and laboratory data. Those subjects that crossed-over to active CPAP will continue.

**Assessment 5.** (wk 36) Those subjects who crossed-over to active CPAP will have their final assessment (after 24 wks of active CPAP) performed as described above. Subject will receive a final debriefing by the Project Manager /Study Coordinator and/or the PI and a copy of their sleep and laboratory data.

Measures to Reduce Attrition. To minimize attrition, in addition to the education/counseling session and telephone calls, we will offer study participants modest monetary compensation for their time. As part of the total compensation, subjects who complete the 12 weeks of CPAP or sham-CPAP when they were blinded to treatment group will receive a \$25 bonus if they were adherent to CPAP for at least an average of 4 hours a night. Subjects who were adherent to CPAP for an average of 6 hours a night will receive an additional \$25 bonus. Subjects who complete the entire study (24 wks) with active-CPAP will receive a maximum compensation of \$270; those on sham-CPAP who then continue to active treatment (36 wks) will receive a total compensation of \$300. Subjects will be compensated after designated assessment time-points. Excluded participants will be compensated for activities they complete.

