**Aim 2 (Secondary):** To determine if CPAP + DEC is superior to sham-CPAP + DEC for improving diabetes self-management outcomes. **H2:** Subjects who receive CPAP + DEC will have better diabetes self-management outcomes (retention of information taught during the DEC classes, improved self-management behaviors, diabetes monitoring activities, increased physical activity, and decreased diabetes-related distress compared to subjects with sham-CPAP + DEC at 6 weeks and 12 weeks).

**Aim 3:** To explore adherence to CPAP (dose) and specific neuro-behavioral and physiological mechanisms (sleep quality, daytime sleepiness, mood, and vigilance that may mediate the effects of CPAP treatment on glycemic control and diabetes self-management outcomes (6 weeks and 12 weeks).

**Aim 4:** To explore the association between the durability of treatment of OSA (i.e. adherence to CPAP) and sleep quality, daytime sleepiness, mood, diabetes self-management, and glycemic control after 24 weeks of active CPAP in the full sample.

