
Analysis Strategy for Aim 2. Using the approach described for Aim 1, repeated measures models will be fitted, and linear contrasts will be estimated to compare 6-week and 12-week values for improvements in diabetes self-management outcomes (retention of information taught during the DEC classes [DKT], improved self-management behaviors [SDSCA], increased physical activity [SenseWare Armband steps], and decreased diabetes-related distress [PAID]) relative to baseline values between subjects on CPAP+DEC and those receiving sham-CPAP+DEC. Generalized linear mixed modeling or nonlinear mixed modeling will be used to analyze longitudinal categorical outcomes should outcome variables need to be categorized for analysis. Along with test statistics and p-values, point and interval estimates will be obtained for linear contrasts.

Analysis Strategy for Aim 3. We will *explore* adherence to CPAP (dose) and specific neuro-behavioral and physiological mechanisms (nighttime sleep, daytime sleepiness, mood, and vigilance during DEC sessions) as possible intervening, or mediator, variables that may mediate the effects of CPAP treatment on glycemic control and diabetes self-management outcomes. Initially, we will fit simple mediational models (predictor, single mediator, single outcome) and estimate whether the effects of CPAP (predictor) on changes in glycemic control and diabetes self-management outcomes are mediated through changes in specific neuro-behavioral and physiological variables (i.e., nighttime sleep, daytime sleepiness, mood, and vigilance during DEC sessions). Standardized parameter estimates of path linkages (with confidence intervals) will be obtained to summarize associations between the exogenous treatment variables, suspected mediators, and distal outcomes, as well as the indirect effect of the treatment group on the targeted outcomes through the suspected mediators and the direct effect of the treatment group on the outcomes. The goodness-of-fit of a model will be assessed using standard summary indices (e.g., RMSEA, CFI) as well as through residual analyses. Depending on the results for testing of individual mediators, we may combine the mediators into a multiple mediator model to develop a more complete picture of these hypothesized mechanisms of action for CPAP.

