**Table 4: Sample Recruitment Monthly Monitoring**

Date				
Total Subjects evaluated				
Subjects randomized				
Men Randomized (month/cumulative)				
Women Randomized (month/cumulative)				
Whites Randomized (month/cumulative)				
Minorities Randomized (month/cumulative)				
Total Randomized Subjects				

Total Goal for Study (to date)				
--------------------------------	--	--	--	--

The PI or Project Manager/Study Coordinator, in accordance with the Institutional Review Board (IRB), will obtain written informed consent for each study subject. Prior to any data collection, we will provide written and oral explanations of the study's purpose, protocol, risks, and benefits. The candidates will have an opportunity to ask questions and then will be asked to sign the form consenting to participate in the study. All advertisements to recruit subjects will be reviewed and approved by the IRB. The study's Steering Committee-(PI, Site PIs and the Co-investigators), as-well as the IRB must agree upon any amendment or revision to the protocol as the trial progresses. One copy of the informed consent form will be given to each subject. One signed copy will be retained in the investigator's study records. At West Virginia University the consent will be scanned into the patient's electronic medical record.

Protection Against Risk - To prevent adverse events this study will follow IRB review and surveillance. The following actions will be taken to protect subjects from risks.

- a) Subjects will be given the National Sleep Foundation "Drowsy Driving Sleep Sheet" to inform them of the risks associated with drowsy driving.
- b) The consent form indicates that subjects should not drive when sleepy. Subjects are informed they should report any falling asleep while driving events to the Project Manager/ Study Coordinator at the time of the monitoring telephone calls during the intervention.
- c) A form called the "Risks of Daytime Sleepiness" will be reviewed with the subject. Questions at the end will be answered to indicate understanding.
- d) After the intervention has been initiated, if a subject report falling asleep while driving, their treatment group will be unblinded and the subject will be withdrawn from the study.
- e) Questionnaires will be completed in the privacy of the subjects' home; they will be instructed to take rest periods as needed if they find completing the questionnaires as burdensome.

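### The Diabetes Knowledge Test, the only measure of retention under H2, appears to be completed unsupervised at home with no closed-book rule, so look-up or help may dilute the between-arm difference

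*Combined protocol and SAP*

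**What the plan says.** **What the DKT is for.** H2 in Specific Aims lists, among the outcomes compared at 6 and 12 weeks, "retention of information taught during the DEC classes, improved self-management behaviors, diabetes monitoring activities". The Analysis Strategy for Aim 2 maps the first of these to one instrument: "retention of information taught during the DEC classes [DKT". No other measure is assigned to it. The Aim 2 measures section gives the DKT 15 items, plus 3 for insulin users, and a duration: "The DKT takes approximately 5-10 minutes to complete". It states no place and no supervision.

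**Where questionnaires are done.**
- Study Measures (under Setting): "questionnaires can be completed in the subject's home at their leisure".
- Assessment 1: "Subjects will be instructed how to complete the questionnaires at home during the next week".
- Assessment 2: "Subjects will be mailed the questionnaires, SenseWear Armband® and the Sleep/Activity/Diet Diary to use for 7-days". Subjects then bring the items back to the site.
- Assessment 3: the questionnaires are again sent out ahead of the visit.
- Protection Against Risk, item e: "Questionnaires will be completed in the privacy of the subjects' home".
- Research Study Compensation: about 1 hour of questionnaires at home.

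**What subjects receive in between.** Diabetes Education/Counseling starts about one week after CPAP or sham begins. On content, "Subject education will be provided using published educational materials". Partners are encouraged to attend, and the educator gives written feedback.

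**The concern.** The other questionnaires used for Aim 2 ask subjects to report on themselves, and private completion at home suits them. The DKT has correct answers. Taken unsupervised over several days, after the education sessions have begun, it can be answered with a booklet open or with a partner who heard the same teaching.

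This bears on the trial's premise. The section on the importance of the knowledge to be gained asks whether sleep disorders act as a barrier to learning self-management, and whether active CPAP increases retention of what is taught. Look-up could mask that difference: a sleepy subject on sham who consults a source may score like a rested subject on active CPAP. A null DKT contrast could then mean no effect on retention, or an effect hidden by the way the test was taken, and the data would not separate the two.

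The baseline DKT is also done at home, but before the trial's own education. Change from baseline could therefore mix learning with access to answers.

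**Working it through.** **1. Does the DKT fall in the home packet?** Every statement that gives a place for the questionnaires as a group gives the home (Study Measures, Assessments 1 to 3, Protection Against Risk, Research Study Compensation). Tests done in person are named individually: the comprehension questions and Newest Vital Sign at Assessment 1, and the PVT-B and Stanford Sleepiness Scale at the education sessions. Besides the return of devices and forms, the site procedures listed at Assessments 2 and 3 are anthropometry and venipuncture, plus the treatment guess and debriefing at Assessment 3. The DKT appears in none of these lists. Home completion is thus the natural reading, though no sentence names the DKT as part of the mailed packet, and the appendix with the instruments is not available.

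**2. The plan's own figure.** Inputs from Sample Size Justification: d = 0.53, two-sided alpha .01, power 0.80, 84 per group, 20% attrition.
- n per group = 2(z₀.₉₉₅ + z₀.₈₀)² / d² = 2(2.576 + 0.842)² / 0.53² = 83.2, rounded up to 84.
- Enrolled = 168 / (1 − 0.20) = 210.
- Power at 84 per group: Φ(0.53·√(84/2) − 2.576) = Φ(3.435 − 2.576) = Φ(0.859) = 0.805. The two-sample t-test gives 0.795.

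The plan's figures reproduce, and nothing here disputes them.

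**3. Illustration of dilution.** Assumption: a fraction q of subjects in both arms look up answers and show no arm difference, with the SD unchanged. The expected difference is then d(1 − q). Neither q nor a DKT effect size is in the documents; 0.53 is the detectable effect for Aim 2 in general.

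| Share lost q | d(1 − q) | Power, normal approximation | Power, t-test |
|---|---|---|---|
| 0% | 0.530 | 0.805 | 0.795 |
| 10% | 0.477 | 0.70 | 0.69 |
| 20% | 0.424 | 0.57 | 0.56 |
| 30% | 0.371 | 0.43 | 0.42 |
| 40% | 0.318 | 0.30 | 0.30 |

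**4. Direction.** Randomization section: subjects and data collectors are blinded, so the opportunity to look up is the same in both arms. Equal look-up pulls the contrast toward zero and does not create a false positive. If the arms differ in how readily subjects look things up, for example because rested subjects make more effort, the score partly measures effort, and the direction is less certain.

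**The case against.** The case against rests on five points.

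- **Inference.** The protocol says that published materials are used in teaching. It does not say that subjects keep them. Instructions for the DKT could sit in the appendix. Both points stand, and they limit the claim to what appears to happen.
- **Incentive.** Nothing shows that look-up occurs. No payment depends on the DKT score; the only performance bonuses are for hours of device use. This stands: contamination is possible, and its frequency is unknown.
- **Baseline.** Randomization balances on previous diabetes education, so some subjects may hold similar materials before the trial's own sessions. This weakens the contrast between baseline and follow-up without removing it.
- **Burden and timing.** Home completion is a deliberate way to spare subjects. Protocol changes dated July 2018 suggest that the trial was already running, so a change of setting partway could confound change from baseline with mode. This stands and shapes the fix.
- **Weight.** The DKT is one of four Aim 2 measures, and Aim 1 is untouched.

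A reader might also infer that contrasts against the pre-class baseline capture only knowledge gained, and that a 6-to-12-week contrast is needed for retention. The documents do not support that. Both arms receive the same standardized education, so a between-arm difference in change from baseline at week 12 reflects taught knowledge still held, an ordinary meaning of retention. The Aim 1 model carried over to Aim 2 already has a time-by-group interaction. A 6-to-12-week contrast would score an arm that learned nothing as having perfect retention, and the follow-up calls have no stated end date, so week 6 is not shown to lie after the teaching.

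**Conclusion.** The point holds in a limited form. The only measure tied to retention appears to be completed at home, unsupervised, with no closed-book instruction, and after education has begun this may contaminate the score and dilute the between-arm difference. A null DKT result would then be hard to interpret.

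It would go too far to call the DKT an open-book test that cannot measure retention. That would require subjects to have the materials at hand and to use them generally, and the documents state neither.

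The size is unknown. The fall in power from 0.80 to between 0.56 and 0.30 rests on an assumed loss of 20% to 40% of d = 0.53, equal in both arms, with unchanged SD. It shows sensitivity and is not an estimate. The sample size, Aim 1 and the other Aim 2 measures are unaffected. If the DKT is already given on site, one sentence saying so closes the matter.

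**What to change.** Take the DKT out of the home packet. Give it closed-book at the existing Assessment 1, 2 and 3 site visits, without partner or teaching materials, and at Assessment 3 before debriefing. Leave the other questionnaires at home.

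At a minimum, add a written no-aids instruction and one item recording any help used. Apply this minimum also to any subject whose baseline DKT was already done at home, and keep that subject's mode the same at every visit, so that change from baseline is not confounded with a change of setting.

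Keep the contrasts in the Analysis Strategy for Aim 2 as they are, and do not add a 6-to-12-week retention contrast.

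The cost is 5 to 10 minutes, by the plan's own figure, within a visit of about 1½ hours, with visit staff on hand during the test. The same 5 to 10 minutes come off the home packet. The sample size does not change.
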